8.5.2 Determination of Drug Concentration

Samples for determination of drug concentration in plasma will be assayed by bioanalytical test sites operated by LabCorp on behalf of AstraZeneca, using an appropriately validated bioanalytical method. Full details of the analytical method used will be described in a separate Bioanalytical Report.

Drug concentration information that would unblind the study will not be reported to investigative study centres or blinded personnel until the study has been unblinded. Only samples from participants on active treatment will be analysed, unless there is a need to confirm that correct treatment has been given to study participants.

Incurred sample reproducibility analysis, if any, will be performed alongside the bioanalysis of the test samples. The results from the evaluation, if performed, may be reported in a separate Bioanalytical Report.

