9.4.4 Exploratory endpoints

9.4.4.1 Exploratory Pharmacokinetic Endpoints

Plasma concentrations of zibotentan and dapagliflozin will be summarised by treatment group, visit, and time-point based on the PKS.

Additional PK analyses may be conducted as appropriate but will be reported outside the CSR.

Further details of this will be provided in the SAP.

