3.2 Analysis Populations

The following analysis sets are defined for the study and detailed in [Table 1](#):

Table 1 **Populations for Analysis**

Population/analysis set	Description
Screened analysis set	All participants who signed the ICF. Unless otherwise stated, the enrolled set will be used for the presentation of disposition data.

Population/analysis set	Description
FAS	All participants who are randomised and receive any study intervention. Participants are evaluated according to the treatment assigned at randomisation. The FAS will be the analysis set for all endpoint analyses with the exception of the PK analyses.
PKS	All participants in the FAS who have at least one detectable zibotentan or dapagliflozin plasma concentration measurement post-treatment. Participants are evaluated according to the treatment assigned at randomisation. Pharmacokinetic samples collected after Visit 5 may be excluded from the PKS and may be reported outside the CSR. The PKS will be used for all PK analyses.

Abbreviations: FAS: Full Analysis Set; ICF: Informed consent form; PKS: Pharmacokinetic Analysis Set; PK: Pharmacokinetics.

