Primary analysis	Absolute change in systolic and diastolic blood pressure from baseline to Week 6.	Estimand population: See above for respective arms. Analysis set: FAS	Treatment policy strategy	Least square mean difference in change from baseline	4.2.5
Exploratory objective 1: To characterise the plasma exposure to zibotentan and dapagliflozin.					
Primary analysis	Plasma concentrations of zibotentan and dapagliflozin.	Estimand population: See above for respective arms. Analysis set: PKS	Treatment policy strategy	Descriptive statistics	4.2.6
Exploratory objective 2: To evaluate the effect of zibotentan/dapagliflozin in combination and zibotentan monotherapy versus placebo on CCI and/or CCI .					
Primary analysis	Percentage and absolute change in CCI and CCI from baseline to Week 6.	Estimand population: See above for respective arms. Analysis set: FAS	Treatment policy strategy	Mean difference between treatment groups	4.2.7
Exploratory objective 3: To evaluate the effect of zibotentan/dapagliflozin and zibotentan monotherapy versus placebo on liver health and portal hypertension biomarkers.					
Primary analysis	
 Percentage and absolute change in AST and ALT from baseline to Week 6. Absolute change in MELD score from baseline to Week 6. 	Estimand population: See above for respective arms. Analysis set: FAS	Treatment policy strategy	Mean difference between treatment groups	4.2.8
Exploratory objective 4: To assess the effect of zibotentan/dapagliflozin in combination and zibotentan monotherapy versus placebo on plasma/serum levels of CCI .					
Primary analysis	Changes in blood and urine biomarkers across time from baseline to Week 6.	Estimand population: See above for respective arms. Analysis set: FAS	Treatment policy strategy	Mean difference between treatment groups	4.2.9

Statistical / Estimand category	Endpoint	Population/Analysis set	Intercurrent event strategy	Population level summary (analysis)	Details in section
Exploratory objective 5: To evaluate the effect of zibotentan/dapagliflozin versus zibotentan monotherapy and placebo on eGFR.					
Primary analysis	Change in eGFR from baseline to Week 6.	Estimand population: See above for respective arms. Analysis set: FAS	Treatment policy strategy	Mean difference between treatment groups	4.2.10

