Exploratory objective 6: To evaluate the effect of zibotentan/dapagliflozin and zibotentan monotherapy versus placebo on fatigue, abdominal symptoms, physical functioning and health-related quality of life					
Primary analysis	Change from baseline to Week 6 in CLDQ Fatigue and Abdominal Symptoms scores, SF-36v2 Physical Functioning score, Total CLDQ score, SF-36v2 Physical Component Summary score, SF-36v2 Mental Component Summary score, Patient Global Impression of Severity - Liver Disease	Estimand population: See above for respective arms. Analysis set: FAS	Treatment policy strategy	Descriptive statistics	4.2.11
Exploratory objective 7: To collect and store plasma, serum and urine samples for exploratory research aimed at exploring biomarkers involved in PK, PD, safety and tolerability related to zibotentan and dapagliflozin in combination versus placebo or CC1					
This objective will not be reported in the CSR.					
-	Evaluation of changes in blood and urine biomarkers	-	-	-	-

a See section [3.3.1.5](#) for details.

For timing of data collection for above endpoints please see SoA in CSP.

Unless otherwise stated the analyses within each section below will be applied for the treatment groups as indicated in the objectives. In general for comparisons of key objectives the following comparisons will be made: zibotentan/dapagliflozin versus zibotentan monotherapy, zibotentan/dapagliflozin versus placebo and zibotentan monotherapy versus placebo.

In case of convergence issues for the analysis model the **CCI** [REDACTED], defined as **CCI** [REDACTED], will be adjusted appropriately to accommodate convergence for the model.

Assessed values of the form ‘<x’ (below the lower limit of quantification) will be imputed as ‘x’ in calculations for key and exploratory objectives.

Subgroup analyses defined in sections below will be done if adequate numbers of observations are available.

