4.2.6.3 Handling of Dropouts and Missing Data

Missing data is assumed to be MAR and no imputation will be done.

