4.2.6.4 Primary Analysis of exploratory objective

The data will be descriptively summarised by treatment group, visit, and time-point. Geometric mean and CV will be presented in addition to arithmetic mean and SD. PK assessments that should only be collected once according to schedule of activities in CSP will be summarised using the assessment closest to target date even if outside of visit windowing.

Additional PK analyses may be conducted as appropriate but will be reported outside the CSR.

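### Results below the limit of quantification are set to the limit in PK and biomarker calculations, with no count of substituted values and no cap on how many a summary may contain

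*SAP*

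**What the plan says.** The rule stands in the general text after Table 7 of SAP 4.2. For assessed values reported as '<x' it reads "below the lower limit of quantification) will be imputed as ‘x’ in calculations for key and exploratory objectives".

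Exploratory objective 1 in that table has the endpoint "Plasma concentrations of zibotentan and dapagliflozin", and exploratory objective 4 covers blood biomarkers, so both fall under the rule. For PK, SAP 4.2.6.4 adds "Geometric mean and CV will be presented in addition to arithmetic mean and SD", and Protocol 9.4.4.1 states "Plasma concentrations of zibotentan and dapagliflozin will be summarised by treatment group, visit, and time-point based on the PKS".

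The only nearby PK provision, SAP 4.2.6.3, is "Missing data is assumed to be MAR and no imputation will be done". That concerns missing data. A '<x' result has been assessed, so it does not displace the rule.

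The PK analysis set (SAP 3.2) is "All participants in the FAS who have at least one detectable zibotentan or dapagliflozin plasma concentration measurement post-treatment". Protocol 8.5.2 limits the assay: "Only samples from participants on active treatment will be analysed, unless there is a need to confirm" that the right treatment was given.

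SAP 4.2.9.4 analyses biomarkers by MMRM on absolute change from baseline, with descriptive summaries by visit. For safety laboratory data, SAP 4.6.3.1 makes the same substitution but keeps '<x' in listings. No such sentence is written for PK or biomarkers.

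**The concern.** The limit of quantification (LLOQ) is the upper bound of what a '<x' result can be. Using it for every result below the limit (BLQ) pushes summaries in a known direction, and with no BLQ count the reader cannot see how far.

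The design can put BLQ samples into the PK tables:

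- Participants who stop treatment stay in the study and attend all visits (Protocol 7.1).
- A PK sample is taken at a visit even when no dose is given (footnote to the Schedule of Activities).
- One detectable value of either drug admits a participant to the PK set, so the participant's other results can all be BLQ.
- Some PK analyses separate Japanese from non-Japanese participants (SAP 4.2.6.6), and Japan contributes up to 5 per arm (Protocol 6.3). One BLQ value among 5 is 20%.

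At stake is whether the exposure tables can be read correctly, and whether a drug effect on a biomarker near its assay limit appears smaller than it is.

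**Working it through.** The plan states no figure that this check could reproduce: no LLOQ, BLQ share or CV is given. The sizes below rest on assumptions. The directions do not.

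**1. Direction at one visit.** The rule is y = max(x, L), where L is the LLOQ. No value falls, so the mean cannot fall relative to the true values. For any two values, |max(a, L) − max(b, L)| ≤ |a − b|, on the raw and the log scale, so the SD and geometric CV cannot rise. In 20,000 random samples of n = 22 the SD was never larger on either scale.

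**2. Size at one visit.** Assume log-normal concentrations with σ = √ln(1 + CV²) and a BLQ share p, and let z be the p-quantile of the standard normal. Then

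geometric mean ratio = exp{σ[p·z + φ(z)]}.

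For CV 50%, σ = √ln 1.25 = 0.472. At p = 20%, z = −0.842 and φ(z) = 0.280, so the bracket is −0.168 + 0.280 = 0.112 and the ratio is exp(0.472 × 0.112) = 1.054.

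| True CV | BLQ share | Geometric mean | Arithmetic SD | Reported geometric CV |
|---|---|---|---|---|
| 50% | 5% | +1.0% | −0.9% | 48% |
| 50% | 20% | +5.4% | −5.4% | 41% |
| 50% | 50% | +20.7% | −19.9% | 28% |
| 100% | 5% | +1.8% | −0.2% | 94% |
| 100% | 20% | +9.7% | −1.7% | 79% |
| 100% | 50% | +39.3% | −8.9% | 52% |

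**3. A cell that is all BLQ.** Every value equals L, so mean = geometric mean = L, SD = 0 and CV = 0%.

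**4. A few participants off drug.** Suppose 2 of 22 have no drug and the other 20 have geometric mean 10 × LLOQ with CV 50%. The simulated arithmetic mean is 10.26 × LLOQ under the rule and 10.17 with zeros (difference 2 × 1/22 = 0.09, under 1%). The SD is 5.98 against 6.13. The geometric mean under the rule is 8.15, while the 20 quantifiable values alone give 10.06. Neither figure tells the reader that 20 were exposed and 2 were not. A BLQ count does.

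**5. Biomarker change.** By the inequality in step 1, no individual change can grow in size. With a simulated 30% fall (CV 50% or 100%, within-subject correlation 0.3 to 0.95), the mean change keeps 0.91 to 0.97 of its true size at 10% baseline BLQ, and 0.73 to 0.88 at 30%. The SD of the change is 0.89 to 1.00 of its true value at correlation 0.3 to 0.5. With CV 50% and 30% BLQ it rises to 1.10 at correlation 0.9 and 1.20 at 0.95.

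**6. Would another substitute be better?** At 20% BLQ and CV 50%, LLOQ/2 gives geometric mean −8.2% and geometric CV 65%, against +5.4% and 41% under the rule (true 50%). At CV 100% it gives −4.4% and 108%, against +9.7% and 79% (true 100%). Neither is better throughout.

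**The case against.** The case for leaving the rule alone has weight:

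- PK and biomarkers are exploratory, and the study has no hypothesis tests.
- With no limits or BLQ shares given, no one can say whether any analyte lies near its limit, and the effect may be nil.
- Choosing a substitute is a convention, and step 6 shows that a common alternative can do worse.

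All of this stands. It bears on severity and on which value to substitute. It does not answer the missing count or the absence of any cap.

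Several stronger readings are tempting but unsupported:

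- **Every undetectable concentration becomes exposure.** Participants with no detectable drug at all are outside the PK set, placebo samples are normally not assayed, and below quantification is not the same as undetectable.
- **The zibotentan-only arm will show dapagliflozin exposure.** Protocol 8.5.2 says whose samples are assayed, not which analyte in which arm. The example holds only if dapagliflozin is assayed there.
- **Evidence of missed treatment is erased.** The rule governs calculations. The SAP does not say raw results are overwritten, and compliance is measured by capsule and tablet counts (SAP 4.1.9).
- **Spread is understated everywhere.** This holds at a single visit. For change from baseline the SD can rise (step 5).

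**Conclusion.** The concern holds for the exploratory PK and biomarker summaries. The rule is explicit, no other section displaces it, and its direction is certain once any true value lies below the limit: single-visit means go up, and single-visit spread cannot increase. Biomarker falls are attenuated. A PK cell that is wholly BLQ would be presented as a precise exposure at the LLOQ.

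The size cannot be determined from the documents. Under the log-normal assumption it is slight at 5% BLQ and material from about 20%. Two unexposed participants among 22 barely move the arithmetic mean when the others are near 10 × LLOQ. The key endpoints (body weight, body water, fat mass, loop diuretics, fluid retention events, blood pressure) have no comparable assay limit, so no key conclusion depends on this.

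**What to change.** - **SAP 4.2:** exclude PK concentrations from the '<x' rule.
- **SAP 4.2.6.4:** report n and % BLQ per analyte, arm and time-point. Show 'NC' for mean, SD, geometric mean and CV when more than half the values are BLQ. Summarise each analyte only in arms assigned it, and list any detectable value found elsewhere. Keep '<x' in listings, as SAP 4.6.3.1 does for safety laboratory data.
- **SAP 4.2.9.4:** show n and % BLQ beside each biomarker summary.

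The section should name the convention for cells with fewer BLQ values, but no particular substitute (LLOQ, LLOQ/2 or 0) need be prescribed, since each is biased in some direction. The cost is SAP wording and a small change to the derivations. The downside is that some cells will read 'NC'. If no BLQ values occur, no estimate changes.

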4.2.1 Key Objective 1 and 2, Composite fluid retention

4.2.1.1 Definition

The estimand is defined in section 4.2.

4.2.1.2 Derivations

The endpoint will be assessed throughout the time period by looking at each observation compared to baseline. For loop-diuretic equivalent derivation see section 3.3.1.5. The composite variable will be yes if any event has occurred on or prior to analyses date.

4.2.1.3 Handling of Dropouts and Missing Data

No imputation will be done.

4.2.1.4 Primary Analysis of key objective

Exact 90% (two-sided) CIs for proportions of participants with the composite of fluid retention in treatment groups will be calculated using the Clopper-Pearson method. The exact unconditional 90% (two-sided) CIs for difference in proportions between the 2 treatment groups compared, as specified in the objectives, will be computed based on score statistic (Chan and Zhang, 1999). **CCI** [REDACTED] will also be presented.

4.2.1.5 Sensitivity Analyses of the key objective

Following analysis for evaluating impact of missing data will be done:

- A conservative imputation approach will be conducted and missing data will be imputed for each component separately except for component of fluid retention AEs and loop-diuretics. For the placebo group, missing data will be imputed as “No event”. For the zibotentan/dapagliflozin and zibotentan monotherapy treatment

groups the missing data will be imputed based on the overall probability for “Event” at a given visit in the combined zibotentan/dapagliflozin and zibotentan monotherapy treatment groups. This probability will be estimated using the observed probability. Seed 3456 will be used. For component of fluid retention AEs, no imputation will be done. For component of loop-diuretics, having no reported loop-diuretics is not considered as missing data. The analyses method will follow section 4.2.1.4.

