Primary analysis	Change in total dosage of loop-diuretic equivalents use from baseline to Week 6 ^a .	
Estimand population: See above for respective arms.
 
Analysis set: FAS.
	Treatment policy strategy	Least square mean difference in change from baseline	4.2.3
Key objective 7: To evaluate the effects of zibotentan/dapagliflozin versus corresponding zibotentan monotherapy on the composite of total body water and total dosage of loop-diuretic equivalents. ^a					
Primary analysis	
Occurrence of either of the two components of this composite:
 
 ● > 3 L increase from baseline in total body water volume 	
Estimand population: See above for respective arms.
 
Analysis set: FAS
	Treatment policy strategy	Risk difference	4.2.4

Statistical / Estimand category	Endpoint	Population/Analysis set	Intercurrent event strategy	Population level summary (analysis)	Details in section
	from baseline to Week 6. 
 • Increase from baseline in 3 or more loop-diuretics equivalents use from baseline to Week 6 ^a. 				
Key objective 8: To evaluate the effects of zibotentan/dapagliflozin and zibotentan monotherapy versus placebo on the composite of total body water and total dosage of loop-diuretic equivalents. ^a					
Primary analysis	Occurrence of either of the two components of this composite: 
 • > 3 L increase from baseline in total body water volume from baseline to Week 6. • Increase from baseline in 3 or more loop-diuretics equivalents use from baseline to Week 6 ^a. 	Estimand population: See above for respective arms. Analysis set: FAS	Treatment policy strategy	Risk difference	4.2.4
Key objective 9: To evaluate the effect of zibotentan/dapagliflozin versus corresponding zibotentan monotherapy on office-based systolic and diastolic blood pressure.					
Primary analysis	Absolute change in systolic and diastolic blood pressure from baseline to Week 6.	Estimand population: See above for respective arms. Analysis set: FAS	Treatment policy strategy	Least square mean difference in change from baseline	4.2.5
Key objective 10: To evaluate the effect of zibotentan/dapagliflozin and zibotentan monotherapy versus placebo on office-based systolic and diastolic blood pressure.					

Statistical / Estimand category	Endpoint	Population/Analysis set	Intercurrent event strategy	Population level summary (analysis)	Details in section

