4.2.3.3 Handling of Dropouts and Missing Data

For missing partial dates for loop-diuretics see section 3.3.1.4. Other missing data is assumed to be MAR and no imputation will be done.

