4.2.4.5 Sensitivity Analyses of the key objective

Following analysis for evaluating impact of missing data will be done:

- A conservative imputation approach will be conducted and missing data will be imputed for each component separately except for component of fluid retention AEs. The placebo group will have missing data imputed as “No event”. For the zibotentan/dapagliflozin and zibotentan monotherapy treatment groups the missing data will be imputed based on the overall probability for “Event” at a given visit in the combined zibotentan/dapagliflozin and zibotentan monotherapy treatment groups. This probability will be estimated using the observed probability. For component of fluid retention AEs, no imputation will be done. The analyses method will follow section 4.2.4.4.

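### SAP 4.2.4.5 exempts a component its composite does not contain and omits the loop-diuretic rule and seed; neither it nor 4.2.1.5 states how many random draws are made

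*SAP*

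**What the plan says.** SAP Table 7 gives the composite for key objectives 7 and 8 two components: "> 3 L increase from baseline in total body water volume" and "Increase from baseline in 3 or more loop-diuretics equivalents use from baseline to Week 6". Fluid retention AEs belong only to the four-component composite of key objectives 1 and 2.

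The sensitivity analysis for the two-component composite (SAP 4.2.4.5) nevertheless says that missing data are "imputed for each component separately except for component of fluid retention AEs. The placebo group will have missing data imputed" as non-events, and later repeats: "For component of fluid retention AEs, no imputation will be done. The analyses method will follow section 4.2.4.4". It does not exempt loop-diuretics and gives no seed.

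The matching section for the four-component composite (SAP 4.2.1.5) exempts both AEs and loop-diuretics, adds "For component of loop-diuretics, having no reported loop-diuretics is not considered as missing data", and ends its description of the draw with "This probability will be estimated using the observed probability. Seed 3456 will be used". It gives no number of imputations.

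Both sections then send the completed data to the primary methods (4.2.1.4 and 4.2.4.4): Clopper-Pearson intervals for proportions and the exact unconditional score interval for a difference, all at 90%. Neither gives a rule for combining imputed datasets. For weight, body water, fat mass and blood pressure, SAP 4.2.2.5 and 4.2.5.5 specify 1000 imputations and a seed.

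**The concern.** There are two separate defects.

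First, the exemption in 4.2.4.5 fits the other composite. Of the two components actually present, neither is protected, so a programmer following the text could impute loop-diuretic events in the active arms while placebo gaps are set to non-events. The same variable would be imputable in one composite and not in the other. No other section repairs this. SAP 4.2.3.3 states "For missing partial dates for loop-diuretics see section 3.3.1.4. Other missing data is assumed to be MAR and no imputation will be done", but it governs key objectives 5 and 6 only.

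Second, a random draw with no stated number of repeats, followed by an interval built for one observed table, reads most naturally as a single imputed dataset. The combination-versus-monotherapy difference then depends on the seed, and the interval carries no allowance for that.

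These are the only planned missing-data checks on the two composites; supplementary analyses are listed as not applicable. What is at stake is how far the checks can be relied on.

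**Working it through.** There is no plan figure to reproduce. The precision statement in Protocol 9.2 is redacted, and the documents give no missingness or event rates. The only design input is about 22 per arm (Protocol 9.2); everything else below is an assumption, shown as a range.

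**Who matters.** Under SAP 4.2.1.2, "The composite variable will be yes if any event has occurred on or prior to analyses date". A participant with an earlier recorded event is therefore already positive, and imputation changes the result only for dropouts who are event-free so far. Call their number *m* per active arm and their imputed event risk *p*. I take *p* from 0.20 (one component at 0.20) to 0.36, which is 1 − (1 − 0.20)² for two components treated as independent.

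**Seed noise in the risk difference.** Imputed events per active arm are Binomial(*m*, *p*), so SD = √(2·*m*·*p*·(1 − *p*)) / 22.

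| *m* per arm | *p* | SD over seeds | Chance that the two arms' imputed counts differ |
|---|---|---|---|
| 1 | 0.20 | √0.32 / 22 = 2.6 points | 32% |
| 1 | 0.36 | √0.4608 / 22 = 3.1 points | 46% |
| 2 | 0.20 | √0.64 / 22 = 3.6 points | 49% |
| 2 | 0.36 | √0.9216 / 22 = 4.4 points | 60% |

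One event is 1/22 = 4.5 points.

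**What one event does to the interval.** Exact unconditional score 90% intervals, 22 per arm, combination minus monotherapy:
- 6 v 10 events: −18.2 points (−41.5 to 6.5)
- 7 v 10 events: −13.6 points (−37.5 to 11.0)
- 6 v 11 events: −22.7 points (−45.5 to 2.0)

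**What the interval leaves out.** The 6 v 10 half-width is 24.0 points, so SE = 24.0 / 1.645 = 14.6. Adding seed variance at *p* = 0.36 gives √(14.6² + 3.1²) / 14.6 = 1.02 for *m* = 1 and √(14.6² + 4.4²) / 14.6 = 1.04 for *m* = 2. The missing width is small; the movement of the point estimate is the larger effect.

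**Repeating the draw.** After 1000 draws the Monte Carlo error of the mean difference is SD / √1000, which is 2.6 / 31.6 = 0.08 points to 4.4 / 31.6 = 0.14 points over the table above.

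**Loop-diuretic gap in 4.2.4.5.** Suppose only dropouts are imputed, with event probability *q* = 0.05 to 0.10, and 0.9 of them are not already positive on body water. The addition per active arm is *m*·*q*·0.9 / 22:
- *m* = 1, *q* = 0.05: 0.2 points
- *m* = 3, *q* = 0.10: 1.2 points

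The addition in placebo is 0.

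**The case against.** **A single draw may be deliberate.** The SAP amendment history records that seeds and the number of imputations were added in the revision. The count of 1000 appears only where multiple imputation is named. A seed fixed in advance is reproducible and cannot be picked afterwards. Both active arms share one pooled probability, so with equal missingness the noise has expectation zero. All of this stands: the issue is noise, not bias. It does not help 4.2.4.5, which has no seed, and it does not make one realisation a good robustness check when repeating it is cheap.

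**Missingness should be low.** Protocol 7.1 keeps participants who stop treatment in the visit schedule, and Protocol 7.2 asks for an early termination visit with Visit 6 assessments. SAP 3.3.2 maps that visit to a window, and the composite Week 6 window is wide (Days 26 to 48). This also stands, and it is why the table stops at two event-free dropouts per arm.

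**Stronger readings that the documents do not support:**
- A reader might infer that every participant with no loop-diuretic record counts as missing in 4.2.4.5. With 10 to 18 such participants of 22, that would add 10 × 0.05 / 22 = 2.3 to 18 × 0.10 / 22 = 8.2 points. But both composites take the variable from the same section (3.3.1.5), and 4.2.1.5 states outright that no reported use is not missing. The omission looks like a drafting slip, not a different rule.
- A reader might infer that the event status being imputed at a visit is undefined, because the composite is cumulative. The text reads naturally as component status at that visit, then cumulated into the composite.
- A reader might infer that setting placebo gaps to non-events is itself a flaw. The SAP declares the approach conservative, and the shift against the active arms is its purpose.

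**Conclusion.** The point holds as a minor correction to two sensitivity analyses. SAP 4.2.4.5 is wrong as written: it names a component its composite lacks and omits the loop-diuretic rule and the seed that 4.2.1.5 contains. The plausible numerical effect is 0.2 to 1.2 points per active arm, assuming 1 to 3 dropouts and an event probability of 0.05 to 0.10. The surplus AE exemption changes no number.

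The undeclared number of draws is the second defect. On the single-draw reading, the combination-versus-monotherapy difference varies by seed with SD 2.6 to 3.1 points (one event-free dropout per active arm) or 3.6 to 4.4 points (two). These figures rest on 22 per arm and assumed imputed risks of 0.20 to 0.36.

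The primary analyses impute nothing (SAP 4.2.1.3 and 4.2.4.3), and no formal tests are planned (SAP 3.3.4). The effect is confined to how much weight these checks can bear.

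**What to change.** In SAP 4.2.4.5, delete both references to fluid retention AEs, copy the loop-diuretic rule from 4.2.1.5 (not imputed; no reported use is not missing) and add a seed.

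In both sections, keep the pooled-probability rule and the placebo rule, but repeat the draw, for example 1000 times as in 4.2.2.5 and 4.2.5.5. Report the mean risk difference, and the spread over draws of both the risk difference and the exact 90% limits.

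If one pooled interval is wanted, use a combining rule suited to small or sparse counts. Rubin's rules with plain binomial variance are a poor choice here. For an expected 6 v 10 events they give half-widths of 23.8 to 25.5 points with 1 to 4 imputed per arm, against 24.0 for the exact interval, so they add little. For 2 v 0 events the plain binomial interval is −1.0 to 19.2 against an exact −4.0 to 25.5, which is too narrow.

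The cost is a few lines of SAP text, a little programming and a slightly longer sensitivity output. The primary analysis does not change. The edit is best made before unblinding.
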